**Summary of Current Year's Enrollment and Drop-out**

Number of participants who signed consent in the past year

45

Did the investigator withdraw participants from the study?

Yes

Circumstances of withdrawal:

Participants consent into the study before completing final eligibility screening; their participation in the study is contingent on passing this final screening. Therefore, meeting exclusion criteria at this point requires withdrawing them from study participation.

Trial: One participant was disqualified from the study after health information request confirmed that participant did not have a history of Hepatitis C infection (an inclusion criterion), despite participant's initial self-report. Five participants were disqualified based on high-risk exclusion criteria, as assessed after consent per protocol (n=4 were at risk for alcohol withdrawal and n=1 affirmed anti-psychosis medication). Risk was assessed according to protocol, appropriate resources were provided, and no emergency referrals were needed.

Did participants decide to discontinue study involvement?

Yes

Circumstances of discontinuation:

Trial: Eight participants consented into the study but could not be scheduled for their baseline appointment despite repeated efforts to contact them and in many cases repeated no-shows. Aside from these 8 participants who did not attend baseline and the 6 withdrawn from the study (enumerated above), all participants completed baseline. Efforts were made to retain participants following baseline, but some were lost to follow-up because they either could not be reached, no-showed, or chose not to attend. However, 31 completed at least one study session. Data collection is now closed.

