#### Exploratory analyses:

Determine whether intervention efficacy differs between these with and without alcohol dependence, and between those with and without alcohol use disorder.

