### Sample #3

Specify subject population

Trial - HIV/HCV co-infected heavy drinkers

Number of completers required to accomplish study aims

We will recruit 80 participants to ensure that 60 meet eligibility criteria and agree to participate. A final sample size of 45 (assuming 75% retention from 60 enrolled patients) is adequate for detecting large differences ( $d=0.85$ ) with 80% power.

Projected number of subjects who will be enrolled to obtain required number of completers

80

Age range of subject population

18-99 (inclusive)

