-Control condition. At baseline, participants will receive brief advice to decrease drinking and a request to spend 20 minutes in the session, observed by the counselor, reviewing an educational pamphlet on drinking, HIV, and HCV. At 30 and 60 days, participants will be asked about their drinking, and again receive advice to decrease drinking. This condition will provide (a) similar exposure time as CG+HealthCall at baseline, (b) brief counselor contact at 30 and 60 days, (c) the same message to decrease drinking, and (d) access to health information. However, the control condition, a realistic approximation of standard-of-care in many places, does not provide in-depth counselor sessions with feedback informed by liver indicators and HealthCall data, the active components of CG+HealthCall for HIV/HCV. This condition was chosen to indicate if CG+HealthCall for HIV/HCV is an improvement over standard-of-care, an important distinction to determine if it warrants further study and eventual dissemination.

-Assessments will precede counselor sessions, and will occur at baseline, 30 days, 60 days, and 90 days (90 days is assessment-only and includes no counselor sessions for either condition). Assessment questionnaires

will be self-administered electronically with the exception of the Timeline Followback and assessment of alcohol use disorder and dependence, which will be administered by the research coordinator or a research team member. The research coordinator/team member will supervise all assessments and answer questions as needed. Efforts will be made to keep the research coordinator/team member blind to condition to minimize potential bias in assessment.

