Understanding and Intervening With Heavy Drinking Among Patients With HIV and HCV

ClinicalTrials.gov identifier: NCT03652675

Analysis Plan excerpt copied from K23 grant proposal finalized May 6, 2014

12.3.2.13. Pilot study: Primary analyses. Chi-squared analyses will assess differences between conditions in gender, ethnicity, age (dichotomized by median split), and education (dichotomized by high school graduation status). If any demographics differ, they will be controlled; otherwise no variables will be controlled. The primary outcome will be drinking quantity (mean drinks per drinking day in the last month), consistent with previous studies of HealthCall^{15,64,92}. Other drinking outcomes (drinking frequency, maximum quantity, frequency of binge drinking) will also be evaluated. I will determine if drinking decreases differentially between the two conditions using mixed effect GLMs, specifying any non-normal (e.g. Poisson) distributions of the outcomes as needed. Power. The sample size (n=45; assuming 75% retention¹⁵) is adequate for detecting large differences (d=0.85) with 80% power. However, as moderate effects were previously found for MI+HealthCall [d=0.44]¹⁵, a moderate effect *even if not significant* would indicate promise for a full trial.

12.3.2.14. Pilot study: Secondary analyses. Interactions. Because previous work found MI+HealthCall to be particularly effective with alcohol dependent patients¹⁵, the sample will be dichotomized by alcohol dependence (AD; DSM-IV)¹¹⁶, and alcohol use disorder (AUD; DSM-5)¹¹⁵ status. To determine if efficacy differs by AD or AUD, I will conduct GLMs for 60-day drinking quantity, with condition, AD or AUD, and their interaction as predictors. Based on previous work at this clinic, ~50% of patients will have AD, with AUD prevalence higher, given the lower threshold. Interactions with gender and ethnicity will also be explored. Changes in readiness to change and self-efficacy. I will assess differential group change in readiness to change and self-efficacy using mixed effect GLMs. Power. I will be able to detect large interaction effects (f=0.52) and large group differences in self-efficacy and readiness to change (d=0.85) with 80% power.

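### The AD/AUD moderator analysis uses day-60 drinking alone, so by default participants who miss that visit do not contribute; the SAP's own mixed model would use their other visits at little cost

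*SAP*

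**What the plan says.** SAP 12.3.2.13 analyses the primary and other drinking outcomes over time: "I will determine if drinking decreases differentially between the two conditions using mixed effect GLMs". SAP 12.3.2.14 treats two secondary outcomes the same way: "I will assess differential group change in readiness to change and self-efficacy using mixed effect GLMs". The moderator analysis in the same section is worded differently: "I will conduct GLMs for 60-day drinking quantity, with condition, AD or AUD, and their interaction as predictors". It names one visit and three predictors, with no random effect, visit term or baseline-drinking term.

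The protocol lists the moderator question under Exploratory analyses: "Determine whether intervention efficacy differs between these with and without alcohol dependence". It sets no visit for it. Under Intervention and Control groups, assessments "will occur at baseline, 30 days, 60 days, and 90 days".

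Loss is planned for (Sample #3: "assuming 75% retention from 60 enrolled patients") and it occurred. The protocol's enrollment and drop-out summary says that after baseline "some were lost to follow-up because they either could not be reached, no-showed, or chose not to attend". Neither document gives an imputation method, a missing-data rule or an analysis population.

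**The concern.** A GLM on one visit can use only people who have a value at that visit. Someone seen at baseline and day 30 but lost before day 60 adds nothing. Nor does someone who misses day 60 but attends day 90. A mixed model fitted to all visits keeps the data that such people did provide.

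Two things are at stake:

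- **Precision.** The test compares four cells, and only 31 trial participants completed a session. That is about 8 per cell before any loss at day 60, so each lost person matters.
- **Bias.** If people who are still drinking heavily at day 30 leave more often in one condition-by-AD cell than in the others, the day-60 mean of that cell is too low among those who stay. The interaction estimate then shifts. The mixed model corrects for this to the extent that the earlier visits explain the dropout.

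**Working it through.** **1. The plan's own figures.** Alpha is not stated; 0.05 two-sided is assumed.
- Retention: 60 x 0.75 = 45, so 15 of 60 are expected to be lost. The visit to which the 75% applies is not given.
- Main comparison: d=0.85 with 22 v 23 gives 79.6% power (noncentral t). This reproduces the stated 80%.
- Interaction: f=0.52 with N=45 and four cells gives 80.6% power with 3 numerator degrees of freedom. This reproduces the stated figure. (A 2x2 interaction has 1 degree of freedom, for which the detectable f at N=45 is 0.43. That is a separate matter.)

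**2. Assumptions.** The documents give neither visit correlations nor day-60 attendance. I assume 25% missing from day 60 on, equal correlation r between visits (0.3 to 0.7), SD 1, four near-equal cells and a normal outcome.

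**3. Standard error of the single-visit interaction.** With four equal cells and n observed in total, SE = sqrt(4/(n/4)) = sqrt(16/n).
- n = 31 x 0.75 = 23.25: sqrt(16/23.25) = 0.83 SD. Simulation, where cell sizes vary by chance, gives about 0.86.
- n = 45: sqrt(16/45) = 0.60 SD. Simulation gives 0.58 to 0.60.

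**4. Precision if loss is random.** Baseline and day 30 together explain R² = 2r²/(1+r) of day-60 variance. Using them multiplies the variance by 1 - 0.25 x R².

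| r | R² | Variance ratio, mixed/GLM | Excess variance of the GLM |
|---|---|---|---|
| 0.3 | 0.18/1.3 = 0.14 | 0.965 | 4% |
| 0.5 | 0.50/1.5 = 0.33 | 0.917 | 9% |
| 0.6 | 0.72/1.6 = 0.45 | 0.888 | 13% |
| 0.7 | 0.98/1.7 = 0.58 | 0.856 | 17% |

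Simulation with 60 participants gives ratios of 0.98, 0.93 and 0.86 at r = 0.3, 0.5 and 0.7. With 31 participants the excess is 4%, 13% and 22% at r = 0.3, 0.6 and 0.7. These use a known covariance. With the covariance estimated at n=31 and r=0.6, the SD falls from 0.87 to 0.83, and (0.87/0.83)² = 1.10, an excess of 10%. The overall range is about 2% to 20%.

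**5. Bias if dropout depends on day-30 drinking in the intervention-AD cell only.** Take a logit slope of 1.5 per SD, with the intercept set for 25% missing. Numerical integration puts the day-30 mean of those who stay at -0.28 SD. The day-60 shift is r times that:
- r=0.3: 0.3 x -0.28 = -0.08 SD
- r=0.6: 0.6 x -0.28 = -0.17 SD
- r=0.7: 0.7 x -0.28 = -0.20 SD

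Simulations of this mechanism give -0.07 to -0.24 SD for the single-visit GLM and 0.02 SD or less for the estimate that uses earlier visits.

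**6. Bias if the same mechanism acts more widely** (n=31, r=0.6, no true interaction). The interaction is a difference of differences, so equal shifts cancel:
- all four cells: 0.00 SD
- both intervention cells: 0.00 SD
- both AD cells: 0.01 SD
- intervention-AD cell only: -0.17 SD

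**7. Size against noise.** 0.17/0.85 = 0.20, a fifth of one standard error. In the one-cell case, two-sided false positives are 5.7%, against 4.7% with random loss.

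**The case against.** Five points can be made for the plan.

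- **The exclusion is inferred.** The SAP is an excerpt from a grant proposal and does not say that people without a day-60 value are left out. That stands as a limit on wording: it is the default result of the model as written, not a stated rule.
- **Day 60 is a legitimate timepoint.** It is the end of treatment and is named in the primary hypothesis. A single visit limits multiplicity, and the exploratory aim need not cover day 90. This stands. The fix therefore keeps day 60 as the main contrast and changes only which data inform it.
- **The mixed model is demanding in so small a sample.** Four cells by four visits is 16 means for about 31 people, and non-AUD cells will be smaller because AUD is expected in more than half. This is a real cost. Even so, with the covariance estimated at n=31 and saturated cell-by-visit means, false positives stayed at 3.5% to 5.5%, and the SD of the day-60 interaction fell in every scenario tried.
- **The inputs are uncertain.** The 31 are those with at least one session; the number randomised is not given. The largest payment falls at day 60 in both arms, which may help attendance at that visit.
- **Little hangs on it.** The trial is a pilot, the analysis is secondary in the SAP and exploratory in the protocol, and no decision rule depends on it. This stands and sets the priority.

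A reader might go further and infer that the 60-day GLM is valid only if missingness is unrelated to drinking within every cell. Or, since the SAP cites earlier work showing more benefit in dependent patients, that dropout bias would pass for confirmation. The documents support neither reading. Shared selection cancels in the interaction, and nothing in the protocol links loss to drinking, arm or AD status. A shift of a fifth of a standard error leaves false positives near 5%.

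**Conclusion.** The inconsistency is in the text. The moderator analysis is a single-visit GLM with no missing-data rule, beside mixed-effect GLMs for the other outcomes. As written, it leaves out anyone without a day-60 value.

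The cost is modest: about 2% to 20% more variance than necessary, and a possible bias of about 0.1 to 0.2 SD against a standard error of about 0.85 SD at n=31. The bias needs drinking-dependent dropout that differs across the condition-by-AD cells. The cancellation shown above is for equal shifts on a linear scale with no true interaction; otherwise it is approximate. All sizes rest on the assumed 25% loss, visit correlations and dropout mechanism.

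This is a low-cost improvement to an exploratory analysis. It does not invalidate the planned one, and it does not make the subgroup question well powered.

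**What to change.** In SAP 12.3.2.14, replace the 60-day GLM as the main moderator analysis with the mixed-effect GLM of 12.3.2.13, adding condition x time x AD (and separately AUD) with the lower-order terms. Include all participants with any drinking assessment. Report the condition-by-AD (or AUD) contrast at day 60 as the main moderator result, with day 90 as supplementary. State the covariance structure and the missing-at-random assumption, and give day-60 attendance by cell. Keep the 60-day GLM as a sensitivity analysis labelled observed-case.

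The cost is a few sentences and a few lines of code on data already collected. The downsides are more mean parameters in a small sample and reliance on missing-at-random. Participants with baseline data only will add little.

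The protocol's continuation report says the data had not yet been analysed. If they have been since, add this analysis and label it post hoc.

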## Lay Summary of Proposed Research

Among patients with HIV, especially those also infected with HCV, heavy drinking is associated with significant risks to health. However, little is known about how to best intervene with co-infected heavy drinkers, a particularly high risk group for whom targeted intervention has not been developed. Therefore, I propose to test a newly developed drinking-reduction intervention for patients with both HIV and HCV, which combines components of successful interventions developed for HIV and for liver disease patients.

We will recruit 80 HIV/HCV co-infected drinkers from HIV primary care in order to ensure 60 eligible and enrolled trial participants, which should yield an adequate final sample size of 45 participants completing the study. Participants will be randomly assigned to an intervention or control condition, while ensuring that equal numbers of individuals with alcohol use disorder are assigned to each condition. The intervention condition will receive brief in-person sessions with a counselor and will be asked to use a smartphone app daily to keep track of drinking and other health behaviors for two months. The intervention sessions will include information about HIV, HCV and alcohol, and the counselor will give the participant information about their liver function and alcohol use to try to motivate them to drink less. The control condition will simply be asked to drink less and will be given pamphlets with general information on HIV, Hepatitis C, and drinking from educational websites on HIV/HCV co-infection. We will then evaluate whether the intervention condition was more effective at reducing drinking than the control condition.

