## TRIAL PROCEDURES

### (1) Explanation of the study and consent

Individuals who appear potentially eligible by the CUMC/NYP clinic recruiter's screening of the medical records or screening through database (recruitment method 1 and 2 as described in the recruitment procedures) and report interest in participating will speak briefly with the research coordinator by phone, who will be trained in human subjects' protections and will ask several simple questions to determine inclusion/exclusion criteria. Individuals who call as a self-referral via flyer or provider (recruitment method 3) will call the research coordinator directly to complete this described phone screening. The research coordinator will meet potential participants at the clinic to obtain informed consent and conduct additional screening for alcohol use disorder status (needed for randomization), as well as psychosis, suicidality, and homicidality, and risk of developing alcohol withdrawal symptoms (final exclusion criteria). Participants ineligible due to psychosis, suicidality, homicidality, and/or being at risk of developing alcohol withdrawal symptoms will be immediately brought to the attention of clinic providers so that they can be appropriately managed; will receive brief advice on alcohol reduction, and referral for help with alcohol abuse if desired or clearly indicated. Eligible participants will be scheduled for a baseline session at either the clinic or the NYSPI offices ([name]), pending space constraints.

In order to obtain participants' health information from their medical records, clinic staff advised that their standard practice of disclosing health information requires written authorization from participants in accordance to HIPAA and CUMC procedures. To comply with this requirement, eligible participants who are patients of the CUMC/NYP clinic will sign an authorization form at time of informed consent allowing clinic staff to disclose requested health information from medical records to research team.

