### (2) Randomization

After participants complete the screening assessment, the research team member will be able to determine alcohol use disorder status from the responses. The research team member will provide the counselor or PI with the participant identification number (ID; assigned consecutively) and alcohol use disorder status. The counselor or PI will then randomize participants using pre-determined blocked lists created by a biostatistician, in order to balance treatment groups across alcohol use disorder status (the research coordinator will not randomize in order to remain blind to condition). Randomization lists were generated (in R software) and provided by biostatistician [name] on May 4, 2018.

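### Randomisation balances alcohol use disorder but only partly balances alcohol dependence, the moderator the SAP cites, and the primary model adjusts for neither

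*SAP*

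**What the plan says.** **Balancing factor.** Protocol, (2) Randomization, uses blocked lists prepared in advance "in order to balance treatment groups across alcohol use disorder status". The Lay Summary states the same aim, "while ensuring that equal numbers of individuals with alcohol use disorder are assigned to each condition". No second factor is named and no block size is given.

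**Moderator.** SAP 12.3.2.14 will examine both AD (DSM-IV) and AUD (DSM-5). The evidence it cites is for AD only: "previous work found MI+HealthCall to be particularly effective with alcohol dependent patients". On prevalence it says: "Based on previous work at this clinic, ~50% of patients will have AD, with AUD prevalence higher, given the lower threshold". The interaction model for 60-day quantity is specified "with condition, AD or AUD, and their interaction as predictors".

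**Primary model.** SAP 12.3.2.13 tests gender, ethnicity, age and education for differences between conditions, adjusts for any that differ, and otherwise adjusts for nothing. Neither AUD nor AD is a candidate covariate. The model asks whether drinking falls by different amounts in the two conditions. The Protocol's Primary Hypothesis instead compares the level of drinking at 60 and 90 days.

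**Measurement.** Protocol, (3) Intervention and Control groups, lists the "Timeline Followback and assessment of alcohol use disorder and dependence, which will be administered by the research coordinator" or another team member, so dependence is already collected.

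**The concern.** A blocked list controls the factor it is blocked on, and controls other variables only through their association with that factor. If most participants have AUD, dependence within that large stratum is left to chance. AD would be expected to relate to how much people drink, and the SAP itself expects it to relate to how well the intervention works. In a small trial the arms could differ on AD, and the planned primary model has no term to correct for it. What is at stake is the point estimate, because the SAP will treat a moderate effect (its reference is d=0.44) as promising even when it is not significant.

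**Working it through.** **Inputs from the documents.** AD about 50%; AUD higher, no figure (SAP 12.3.2.14). 60 to be randomised, about 30 per arm (Protocol, (3) Intervention and Control groups). 31 completed at least one session (Protocol, Overall Progress).

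**Assumptions.** AUD prevalence 60% to 90%. Everyone with AD also has AUD. Arms of 16 and 15 at n=31. The exact calculation takes AUD counts as balanced between arms; the simulation uses permuted blocks of 4.

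**1. The plan's own figure.** 60 × 0.75 = 45. With 22 and 23 per arm, d=0.85 and two-sided 5% (assumed), power is 79.6% by the t test and 81.4% by the normal approximation. The stated 80% reproduces, so the sample-size statement is not in question here.

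**2. Size of a chance AD gap.** Let p be AUD prevalence, q = 0.5/p the AD share among those with AUD, and m = 30p the AUD participants per arm. With AUD balanced, the SD of the gap in AD share is √(2mq(1−q))/30.

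- p=0.6: q=0.833, m=18, SD = √(2×18×0.139)/30 = 7.5 points.
- p=0.9: q=0.556, m=27, SD = √(2×27×0.247)/30 = 12.2 points.
- No stratification: √(2×30×0.25)/30 = 12.9 points.

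Probability of a gap of 20 points or more, exact (simulated in brackets):

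| AUD prevalence | SD, n=60 | P, n=60 | SD, n=31 | P, n=31 |
|---|---|---|---|---|
| 60% | 7.5 | 1.4% (1.6%) | 10.7 | 6.7% (7%) |
| 70% | 9.8 | 5.9% (5.4%) | 13.4 | 14.6% (16%) |
| 80% | 11.2 | 10.0% (9.7%) | 15.6 | 21.5% (22%) |
| 90% | 12.2 | 13.1% (12.2%) | 17.3 | 26.2% (27%) |
| No stratification | 12.9 | 15.5% (15%) | 18.0 | 28.1% (29%) |

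With lists blocked on three levels (no AUD / AUD without AD / AD), the simulated probability is essentially zero at both sizes.

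**3. Effect on an unadjusted comparison at 60 or 90 days.** Shift = gap × AD effect. The documents give no AD effect on drinking, so 0.3 to 1.0 SD is assumed. A 20-point gap gives 0.20×0.3 = 0.06 SD, 0.20×0.5 = 0.10 SD and 0.20×1.0 = 0.20 SD. Against d=0.44 these are 14%, 23% and 45%. The standard error of a standardised difference at n=31 is √(1/16+1/15) = 0.36, so even the largest shift is 0.20/0.36 = 56% of one standard error.

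**4. Effect in a differential-change model.** Suppose AD adds the same amount δ at every visit. A gap g then moves the arm difference by gδ at baseline and by gδ at follow-up, and the change contrast moves by gδ − gδ = 0. With a log link the same holds if AD acts as a constant ratio. What does not cancel is a different rate of change in AD participants, or a larger treatment effect in them.

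**5. Effect on the AD interaction test.** AD is already a main effect in that model. At n=45, with power set to 80% when AD is balanced, a 20-point gap gives 78.4% and a 30-point gap 76.2%.

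**The case against.** The strongest reply is that AUD is a legitimate blocking factor. Both AD and AUD are named moderators, and a pilot of 60 cannot block on everything. Chance imbalance under valid randomisation is part of sampling error, which the standard error already covers; it is not bias. All of this stands.

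Three stronger readings are tempting, and the documents do not support them.

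- *AUD blocking does little for AD.* At the planned 60 it cuts the risk of a 20-point gap from about 15% to 1.4% or 5.9% when AUD prevalence is 60% or 70%. Protection nearly disappears only towards 90%, and no AUD prevalence is stated.
- *An AD gap passes straight into the primary result.* That is true of an unadjusted comparison of levels, as the Protocol's Primary Hypothesis is worded. It is not true of the differential-change model in SAP 12.3.2.13, where a stable difference largely cancels. Evidence that AD modifies the treatment effect also does not say how much AD shifts drinking.
- *The moderator analysis is compromised.* Uneven cells cost about 2 points of power at a 20-point gap.

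It is also fair to say that new lists are no longer possible, since the Protocol reports data collection complete. Nor is it certain that dependence could have been scored in time: the Protocol's consent section mentions only AUD status as the screening item needed for randomisation.

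**Conclusion.** The point holds as a minor one. AD is balanced only indirectly, and the primary model leaves out both the randomisation factor and a baseline severity measure that is already collected. A 20-point AD gap is a minority event: about 2% to 12% at 60 and 7% to 27% at 31, for AUD prevalence of 60% to 90%. If it occurred, it would move an unadjusted 60- or 90-day comparison by about 0.06 to 0.20 SD. The documents do not show that a gap did occur.

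These figures rest on AD being nested in AUD, on an assumed block size and AUD prevalence, and on an assumed AD effect. At AUD prevalence of 55% the SD of the gap at n=60 is only 5.4 points. The n=31 figures also treat the blocks as intact. Randomisation follows screening, so if any of the eight people who never attended baseline had been randomised, balance among the 31 would be looser than shown.

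**What to change.** The Protocol's continuation summary says the data have not yet been analysed, so the model can still be fixed in advance. In SAP 12.3.2.13, replace the clause that leaves everything except differing demographics unadjusted with these rules:

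- The primary model always includes baseline alcohol severity as a three-level factor: no AUD, AUD without AD, AD. This carries the randomisation factor and adds AD.
- A level with very few participants is merged with its neighbour, by a rule set on counts pooled over arms before outcomes are examined. This is likely to be needed: at n=31, AUD of 90% leaves 0.10×31, about 3 people, without AUD, and AUD of 60% leaves about 3 with AUD but not AD.
- Where the model estimates differential change, the factor's interaction with time is included. A main effect alone would not correct a different course in AD participants.
- AD is reported by arm.

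**Cost.** One or two extra parameters per time effect at n=31. The precision gain is small: the standard error falls by roughly 0 to 5% for an assumed AD effect of 0.3 to 0.8 SD. The benefit is mainly that a chance AD gap can no longer explain the result. Baseline AD must also be available for everyone analysed; the measures table that would confirm this is an attachment not reproduced in the Protocol.

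Had randomisation still been open, three-level lists would have kept AUD balance and added AD balance, provided dependence could be scored at screening. The price would have been arm sizes possibly unequal by a few participants.
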